2.4 Feasibility and Pilot Endpoints

CHRONOS-A and CHRONOS-B Pilot Outcome Measures

Primary

 Feasibility and acceptance of randomisation (rate per-month per-centre averaged) and compliance to allocated arm.

Secondary

IP4 - CHRONOS 19CX5006 Imperial College London Date: 13th July 2022	Short Title: IP4 - CHRONOS	Protocol No: 19CX5006	Sponsor: Imperial College London	
---	-------------------------------	--------------------------	-------------------------------------	--

- Patients' experience of consent and recruitment, including reasons for declining participation.
- Patients' motivation to accept randomisation to, and compliance with an intervention and understanding of each trial arm.
- Patients' experience of each arm including systemic issues, erectile dysfunction, urinary symptoms and rectal symptoms.
- Healthcare professionals' attitudes to intervention arms and trial design and whether this might impact on recruitment.
- Potential improvements to recruitment processes.
- To establish the feasibility of an economic evaluation alongside the main trial.

Feasibility will be measured based on a point-estimate of recruitment rates. Eligibility will be assessed against pre-defined eligibility criteria. The reasons for ineligibility will be recorded and compared across CHRONOS-A and CHRONOS-B. The retention/compliance rate will be defined as the number of participants completing study interventions and any follow-up imaging and biopsy. The reasons for withdrawal will be documented with a questionnaire given to individuals.

The integrated qualitative component is designed to inform the primary and secondary trial objectives in the trial recruitment and testing stages. Participant interview data highlighting trial processes in need of improvement may be used in real time to allow timely protocol amendments in order to improve recruitment and retention of participants. We will also interview healthcare professionals (physicians, nurses) responsible for recruiting patients.

2.5 Main Study Primary Endpoints

CHRONOS-A

Progression-Free Survival (PFS) with progression defined as biochemical failure (radical therapies only), salvage therapy (local or systemic) or prostate cancer metastases or prostate cancer specific mortality. Salvage local therapy following focal therapy will be defined as surgery or radiotherapy or 3 or more focal therapy sessions. Any radiotherapy given after prostatectomy will be counted as an event.

CHRONOS-B

Failure-Free survival (FFS) with failure defined as time to one further focal therapy session or salvage therapy (local radiotherapy or surgery, or systemic) or prostate cancer metastases or prostate cancer specific mortality.

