- Arm 2 (Intervention): Focal therapy alone (high intensity focused ultrasound [HIFU] or cryotherapy as per physician and centre choice). A second focal therapy session in-field, or a first focal therapy session to an out-of-field progressive or de novo lesion will be allowed as part of the focal therapy intervention.

CHRONOS-B

- Arm 1 (Control): Focal therapy alone (high intensity focused ultrasound [HIFU] or cryotherapy as per physician and centre choice). A second treatment infield, or a first focal ablation to an out-of-field progressive or de novo lesion will be allowed but will be regarded as failure events for the purpose of CHRONOS-B.
- Arm 2 (Intervention): Neoadjuvant finasteride 5mg once daily for a minimum of 12 weeks followed by focal therapy (as per control arm).
- Arm 3 (Intervention): Neoadjuvant bicalutamide 50mg once daily therapy for a minimum of 12 weeks followed by focal therapy (as per control arm). Other arms can be added in future with protocol amendments.

Protocol No:	Sponsor:	Version: 5.0
19CX5006	imperial College London	Date:
		13 th July 2022
	Protocol No: 19CX5006	

FEASIBILITY	CHRONOS-A and CHRONOS-B Pilot Outcome Measures		
AND PILOT STUDY	Primary		
ENDPOINTS	Feasibility and acceptance of randomisation (rate per -month, per -centre)		
	averaged) and compliance to allocated arm.		
	Secondary Patients' experience of concept and regruitment, including reasons for		
	 Patients' experience of consent and recruitment, including reasons for declining participation. 		
	Patients' motivation to accept randomisation to, and compliance with an		
	intervention and understanding of each trial arm.		
	Patients' experience of each arm including systemic issues, erectile dysfunction, urinary symptoms and rectal symptoms.		
	Healthcare professionals' attitudes to intervention arms and trial design		
	and whether this might impact on recruitment.		
	Proportion of patients successfully recruited into each of CHRONOS-A and		
	CHRONOS-B		
	 Potential improvements to recruitment processes. To establish the feasibility of an economic evaluation alongside the main 		
	trial.		
PRIMARY	CHRONOS-A: Progression-Free survival (PFS) defined as biochemical failure		
ENDPOINTS	(radical therapies only) or salvage therapy (local or systemic) or prostate cancer		
(Main Stage)	metastases or prostate cancer specific mortality.		
	CHRONOS-B: Failure-Free survival (FFS) defined as more than one focal therapy		

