2.2 Main Study Primary Objectives

CHRONOS-A

To evaluate progression-free survival (PFS) rates of focal therapy alone compared to radical therapy (radiotherapy or surgery) in the treatment of non-metastatic clinically significant prostate cancer. PFS is defined as time from randomisation to salvage whole-gland or systemic therapy, prostate cancer metastases or prostate cancer-specific mortality.

CHRONOS-B

Short Title: IP4 - CHRONOS	Protocol No: 19CX5006	Sponsor: Imperial College London	Version: 5.0 Date: 13 th July 2022
			-

• To evaluate Failure-Free-Survival (FFS) rates of focal therapy alone compared to focal therapy combined with other therapies as a neoadjuvant strategy. FFS is defined as time from randomisation to further focal therapy session or salvage whole-gland or systemic therapy or prostate cancer metastases or prostate cancer-specific mortality.

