- As there is no defined time-point for a PSA nadir value following FT the PSA value at 12-months post randomisation in patients with a negative MRI will be used. Following this if there are any two further consecutive rises in PSA at least 3 months apart, with no influencing factors at the time (e.g., urinary tract infection, instrumentation/procedures, biopsies, catheterisation), a for-cause mpMRI with or without biopsies can be carried out at the discretion of the treating clinician. The Focal Therapy Sub-Group should be informed of this and a review of the for-cause mpMRI findings prior to biopsy should be carried out. Clinically significant prostate cancer in-field that is suitable for further FT should be offered to patients as a routine. Radical therapy should be only recommended to patients in instances where further FT is not suitable. Such situations should only occur after the Focal Therapy Subgroup has reviewed the case as expertise for such decisions may not reside in the local centre.
- In CHRONOS A, a second treatment either in-field or out-of-field will not be classified as failure and is part of the overall focal therapy intervention. In patients who undergo a second treatment of FT the nadir value will be defined at the 12-month time point after the second treatment, provided mpMRI and biopsy targeted at treated area(s) are negative for clinically significant prostate cancer.

Radiotherapy/ Brachytherapy

 In patients where there is suspected PSA relapse but the international definition of biochemical failure (PSA nadir plus 2.0ng/ml) has not been reached, evaluation should include a for-cause mpMRI and biopsy if required. Staging scans should be done as

Short Title: IP4 - CHRONOS	Protocol No: 19CX5006	Sponsor: Imperial College London	Version: 5.0 Date: 13 th July 2022
			10 daily 2022

per local practice. Where salvage local or systemic therapy is given, this will be regarded as PFS event.

Surgery

- Adjuvant or salvage radiotherapy will be regarded as a PFS event and will be determined based on histological findings and PSA kinetics even if the biochemical failure definition is not reached (PSA >/=0.2ng/ml). Staging scans should be done as per local practice.
- Biochemical failure following radical therapy as internationally defined, even if salvage therapy is not given, will be counted as an event for PFS/FFS analyses.

Collection of postcodes

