8.1.2 Main study

Sample size calculations below are for the full phase II studies based on progression-free survival (PFS):

CHRONOS-A: Progression-free survival (PFS) in our population at 5-years is approximately 85-90% after radiotherapy and similar for prostatectomy. Overall survival is high and being a 10-15 year outcome it will not be used in this study. PFS is a clinically meaningful endpoint, with precedence in other studies and can be measured in the same way in both arms (time to salvage therapies). Our hypothesis is that FT is non-inferior in terms of PFS, whilst having fewer side-effects. The question is what margin of non-inferiority should be in the main study. In the CHHIP radiotherapy RCT a 20% relative change was acceptable as a non-inferiority margin comparing one form of radiotherapy to another form of radiotherapy HR 1.208; absolute difference 5%). In the PART RCT pilot (prostatectomy versus FT), a failure of 25% (PFS 75%) for surgery compared to a maximum 35% after focal (PFS 65%) was accepted by the NIHR-HTA as a non-inferior design because the functional detriment would be substantially better.

For a patients' perspective, we can look at the unpublished NCRN COMPARE study (presented at NCRI UK Annual Conference, November 2018). This was a discrete choice experiment where 544 newly diagnosed men (~30 UK centres) were asked to make choices between different treatment scenarios. Marginal Rate of Substitution (MRS) were calculated (trade-offs men are willing to make between side-effects and survival). On average men are willing to trade 0.68% of survival chance against 1% chance of improving urinary function, with PFS and sexual function MRS at 0.41% and 0.28%. Based on the above, it is reasonable to assume 85% PFS after radiotherapy with a non-inferiority margin of 5% for FT would meet clinical and patient acceptance.

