Based on an allocation ratio of 1:1 and a non-inferiority margin of 0.05 with a 0.85 PFS rate in the standard care arm (at median 5-years), power 0.80 and alpha 0.05, drop-out after randomisation of 5%, the overall required sample size is 1190 with 136 expected total number of events. Total recruitment and follow-up period will be 8 years. If recruitment rates were deemed to be high then the power could be adjusted to 0.90 and the total sample size will be 1660 with 189 expected total number of events. This will be on the advisement of the TSC. PFS for the main Stage will be defined as transition to salvage therapies or metastases or mortality related to prostate cancer.

CHRONOS-B main stages II and III: Using the latest update of –nstage-, with an allocation ratio of 1:1:1, we anticipate approximately 1200 patients are required over 5 years to observe 120 control arm failure-free survival (FFS) events within 7.6 years. This time will be dependent on observed FFS event rates and is based on an assumption of 20 patients recruited per month. This calculation gives 85% power at the efficacy stage analysis, to detect a hazard ratio (HR) of 0.67 and is based on 20% of patients having a FFS event by 3 years (30% by 5-years).

Table 1. Sample size calculations

	Short Title: IP4 - CHRONOS	Protocol No: 19CX5006	Sponsor: Imperial College London	Version: 5.0 Date: 13 th July 2022
١				10 Gary Lore

	Stage 1	Stage 2	Overall
Alpha	0.45	0.025	0.044
Power	95%	85%	83%
Critical HR (guidance for stopping early)	0.974		-
Control Arm Events	47	120	-
Accrual	20pts/m	20pts/m	20pts/m
Cumulative Patients	1003	1200	-
Time to analysis (years)	3.4	4.2	7.6

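### CHRONOS-A states its primary endpoint in two ways: biochemical failure after radical therapy is a PFS event in three places and is absent from the definition in two others

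*Protocol*

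**What the plan says.** Three places in the protocol make biochemical failure after radical therapy a PFS event:

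- Trial Summary, Primary Endpoints: "Progression-Free survival (PFS) defined as biochemical failure", limited to radical therapies, or salvage, metastases or prostate cancer death.
- Section 2.5: "Progression-Free Survival (PFS) with progression defined as biochemical failure (radical therapies only), salvage therapy (local or systemic) or prostate cancer metastases", or prostate cancer death.
- Section 5.9 (Surgery): "Biochemical failure following radical therapy as internationally defined, even if salvage therapy is not given, will be counted as an event for PFS/FFS analyses".

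Two places define PFS without it:

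- Section 2.2: "PFS is defined as time from randomisation to salvage whole-gland or systemic therapy, prostate cancer metastases or prostate cancer-specific mortality".
- Section 8.1.2: "PFS for the main Stage will be defined as transition to salvage therapies or metastases or mortality related to prostate cancer".

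Section 8.1.2 also justifies the choice of PFS because it "can be measured in the same way in both arms (time to salvage therapies").

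Section 2.5 adds salvage rules that differ by arm. In the focal arm, "Salvage local therapy following focal therapy will be defined as surgery or radiotherapy or 3 or more focal therapy sessions". After surgery, "Any radiotherapy given after prostatectomy will be counted as an event". Section 5.9 (Biochemical Failure) explains why the focal arm has no PSA event: no such definition has been validated after focal therapy.

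The SAP supplied covers the feasibility stage only and defines no PFS event. That is not a fault in it, but it cannot settle the question.

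**The concern.** Take a man in the radical arm whose PSA meets the biochemical failure definition and who receives no salvage treatment. Under 2.5 and 5.9 he has progressed. Under 2.2 and 8.1.2 he is progression-free. Two analysts working from different sections would count different primary events.

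The focal arm has a smaller version of the same problem. Section 2.2 restricts local salvage to whole-gland treatment, so a third focal session is not an event there, although 2.5 makes it one.

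The comparison is a non-inferiority one. An event that can occur only in the control arm lowers control PFS and, taken alone, makes focal therapy look closer to radical therapy. The protocol does not say whether the 0.85 control rate and the 0.05 margin were set with that event included.

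**Working it through.** **1. The definitions side by side**

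| Protocol place | Biochemical failure (radical arm) | Third focal session (focal arm) |
|---|---|---|
| Trial Summary | event | salvage not detailed |
| 2.5 | event | event |
| 5.9 | event, even without salvage | not the issue there |
| 2.2 | not listed | not an event (whole-gland salvage only) |
| 8.1.2 | not listed | salvage not detailed |

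**2. The symmetry statement.** Under 2.5, biochemical failure can be an event only in the radical arm, the session count applies only after focal therapy, and the radiotherapy rule applies only after prostatectomy. The statement in 8.1.2 is therefore wrong under 2.5. The salvage rules would remain arm-specific even if biochemical failure were dropped.

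**3. The plan's own figure.** Section 8.1.2 gives 1190 patients and 136 events for control PFS 0.85, margin 0.05, power 0.80, alpha 0.05 (sidedness not stated) and 5% drop-out. With one-sided 0.05, the formula 2 × (1.645 + 0.842)² × 2 × 0.85 × 0.15 / 0.05² gives 1262 in total before drop-out and 1329 after (1262/0.95). The margin hazard ratio is ln 0.80 / ln 0.85 = 1.373, which needs 247 events by Schoenfeld's formula. The stated figures are not reproduced. That is a separate matter, so the illustration below takes 1190 as given.

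**4. Illustration of the control-only event**

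Inputs from 8.1.2: evaluable per arm = 1190 × 0.95 / 2 ≈ 565; margin 0.05.

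Assumptions, not in the documents:
- alpha 0.05 is one-sided (z = 1.645);
- salvage-based PFS is truly 0.85 in the radical arm and 0.80 in the focal arm, exactly at the margin;
- a share x of radical-arm men have biochemical failure without salvage, so counted control PFS is 0.85 − x.

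SE = √[(0.85 − x)(0.15 + x)/565 + 0.80 × 0.20/565]

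P(declare non-inferiority) = Φ(x/SE − 1.645)

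| x | Men of 565 | SE | x/SE | P |
|---|---|---|---|---|
| 0 | 0 | 0.02256 | 0 | 0.050 |
| 0.01 | about 6 | 0.02283 | 0.438 | 0.114 |
| 0.02 | about 11 | 0.02309 | 0.866 | 0.218 |
| 0.03 | about 17 | 0.02333 | 1.286 | 0.360 |

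On the hazard ratio scale, P = Φ((ln 1.373 − ln HR) × √d / 2 − 1.645), with d = 136 events as planned. The hazard ratio is 1.280 to 1.297 at 1 point and 1.124 to 1.147 at 3 points, depending on which definition carries the 0.85. This gives about 9 to 11% at 1 point and 28 to 32% at 3 points. The direction is the same and the size somewhat smaller.

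**5. Why the definition behind 0.85 matters.** If 0.85 already includes biochemical failure, salvage-based control PFS is higher. The formula in step 3 then gives 1192, 1120 or 1046 in total before drop-out at 0.86, 0.87 or 0.88, against 1262 at 0.85.

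**The case against.** **The protocol does lean one way.** Section 5.9 rules on exactly the disputed patient. It also sets confirmation and dating rules for biochemical failure and, where salvage comes first, asks for the nearest earlier PSA as the progression value. The section headed Primary Endpoints and the Trial Summary agree. The outliers are an objective and a closing sentence on sample size. This stands: a reader might infer that the primary event is wholly undetermined, and that goes too far. But both outliers are worded as definitions, nothing gives precedence, and one sits beside the control rate and margin.

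**Bias towards non-inferiority.** A reader might infer that 2.5 biases the trial that way overall. The documents do not establish a net direction. Only the focal arm has protocol-led imaging, at 12 months, which could bring focal-arm events to light. Section 5.9 also limits when radical therapy is recommended after focal therapy, which could hold such events back. The figures in step 4 describe an error only if the salvage-based definition is the intended one.

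**Lost salvage data.** A reader might infer that salvage after biochemical failure would go unrecorded, because 5.9 ends PSA testing at progression. That rule stops PSA testing, not the recording of salvage. Section 2.6 makes salvage treatments and prostate cancer mortality secondary endpoints, 2.7 evaluates them to 5 years, and 5.7 schedules six-monthly visits to 60 months.

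**A double requirement.** A reader might want the salvage-based bound also to exclude the margin before non-inferiority is claimed. In step 4's model, 2.5 only adds control-arm events, so the salvage-based analysis would decide every claim. That replaces the endpoint. In 400,000 simulated trials with arms equal on 2.5, power fell from 76% to about 26% at a 3-point share.

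**Conclusion.** The inconsistency is real and follows from the text alone. Three places count biochemical failure after radical therapy, two define PFS without it, and the justification in 8.1.2 is untrue under 2.5. The specific event rules favour inclusion, but the protocol does not say that they prevail.

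The size of the consequence is unknown. The 11, 22 and 36% in step 4 rest on assumed shares of 1, 2 and 3 points, a true 5-point deficit on the salvage-based definition, 565 men per arm and a one-sided 5% test. They show that a small share can matter and are not estimates for this trial.

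The main stage depends on funding and the pilot decision does not use PFS, so nothing in the feasibility analysis changes. The definition must be settled before any main-stage PFS analysis.

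A related conflict needs settling with it. Section 5.8 calls hemiablation of the second lobe, after hemiablation of the first, a failure of focal therapy. Section 5.9 says that a second treatment in CHRONOS-A, in-field or out-of-field, is not failure. The 5.8 text may be a specific exception, but it does not say so, nor whether its failure is a PFS event.

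**What to change.** Before any main-stage PFS analysis:

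1. State one PFS definition identically in the Trial Summary, 2.2, 2.5, 5.9 and 8.1.2. The simplest course is to align 2.2 and 8.1.2 with 2.5, including its rule on focal sessions.
2. Delete or correct the statement in 8.1.2 that PFS is measured alike in both arms.
3. Confirm that the 0.85 control rate and the 0.05 margin refer to the definition kept.
4. Pre-specify and report the same non-inferiority comparison on the salvage-based definition (salvage, metastases, prostate cancer death). Make it a supportive sensitivity analysis, not a gate on the claim. The data are already planned to 5 years.
5. Reconcile 5.8 and 5.9 on whether contralateral hemiablation after hemiablation counts as a PFS event.

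The cost is a protocol amendment and one extra analysis. No new data collection is needed.

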2.6 Main Study Secondary Endpoints

Disease control

- Rates of positive biopsy for any cancer and significant cancer defined by a number of different thresholds on biopsy following focal therapy (treated and untreated side).
- Rates of second or third focal therapy sessions, in-field or out-of-field.
- Rates of radiotherapy as adjuvant or salvage therapy following surgery or focal therapy.
- Rates of prostatectomy as adjuvant or salvage therapy following radiotherapy or focal therapy.
- Rates of systemic therapy as adjuvant or salvage therapy following surgery, radiotherapy or focal therapy.
- Rates of prostate cancer-specific mortality.

IP4 - CHRONOS 19CX5006 Imperial College London Date: 13th July 2022	Short Title: IP4 - CHRONOS	Protocol No: 19CX5006	Sponsor: Imperial College London	
---	-------------------------------	--------------------------	-------------------------------------	--

- Rates of all cause mortality.
- Long-term health outcomes of those participants consenting to longitudinal follow-up will be reported in subsequent studies pending further funding.

Adverse events and functional outcomes

- Rates of cystoscopic interventions following treatment.
- Rates of implant insertion for treatment of incontinence and erectile dysfunction.
- Rates of medication and/or pump devices used for erectile dysfunction following treatment.
- Rates of endoscopic investigations of the lower bowel following treatment.
- Rates of pad-use and quantity per day for urinary incontinence following treatment.
- Rates of pad-use and quantity per day for faecal incontinence following treatment.
- Rates of adverse event rates and complications.
- Genito-urinary & rectal side-effects using patient-reported outcome measures using validated questionnaires (EQ-5D-5L, International Index of Erectile Function-15, EPIC-26, EPIC Urinary domain, International Prostate Symptom Score and CTCAEv4.0 bowel domain) including evaluation of return to baseline function for erectile and urinary function and various minimum decreases in PROMS scores as defined for IIEF and IPSS in the literature that might be clinically relevant.

Health economics

- To establish the NHS costs of the different interventions.
- The incremental cost per quality adjusted life year (QALYs) gained over the estimated lifetime of participants for focal therapy versus radical therapy.
- The incremental cost per quality adjusted life year (QALYs) gained over the estimated lifetime of participants for focal therapy versus focal therapy with neoadjuvant strategy.

Qualitative

- The impact on participants' overall health-related quality-of-life as well as adverse events and impact on genito-urinary and rectal functional status using validated patient reported outcome measures.
- Descriptive analyses of the questionnaire data, and use of questionnaire and qualitative interview datasets in a multi-methods analysis to look for overarching themes in barriers and facilitators to participation in CHRONOS-A and CHRONOS-B.

Imaging and Pathology

• Accuracy and variability of multi-parametric MRI in detecting disease at baseline prior to focal therapy and absence or presence of recurrence of cancer based on histology outcomes on biopsy. Target definition for recurrence will be defined as significant prostate cancer as per inclusion criteria.

Translational, Biobank and Databank

- Analysis on the localisation and nature of cancer-infiltrating immune cells and the immune-relevant gene expression within the cancer tissue.
- The creation of a biobank and databank of matched blood, serum, plasma and predigital rectal examination urine as well as imaging as well as FFPE biopsy samples (diagnostic samples before entry into trial and subsequent prostate, prostatectomy, and distant site samples carried out post-treatment) will be built for future validation and development of other biomarker panels as well as educational purposes. To be carried out prior to treatment and at defined points after treatment.

